Secondary Endpoints	1) mRS score improvement at 90 ≠ days (shift analysis); 2) Proportion of patients with mRS score 0 to 4 at 90 ≠ days (%); 3) Proportion of patients with mRS score 0 to 3 at 90 ≠ days (%); 4) Proportion of patients with mRS score 0 to 2 at 90 ≠ days (%); 5) Proportion of patients with mRS score 0 to 1 at 90 ≠ days (%); 6) mRS score improvement at 1 year (shift analysis); 7) Proportion of patients with mRS score 0 to 2 at 1 year (%); 8) Proportion of patients with mRS score 0 to 1 at 1 year (%); 9) mRS score improvement at 5 years (shift analysis); 10) Proportion of patients with mRS score 0 to 2 at 5 years (%); 11) Proportion of patients with mRS score 0 to 1 at 5 years (%); 12) NIHSS score at 5-7 days or at early discharge; 13) Health-related quality of life [European Quality of Life Five-Dimension visual-analogue scale (EQ-5D VAS)] at 90 ≠ days; 14) Proportion of patients with malignant cerebral edema within 48 hours after EVT (%) 15) Proportion of patients with secondary decompressive craniectomy(%) 16) EQ-5D VAS at 1 year;		
	17) EQ-5D VAS at 5 years.		
Safety Endpoints			
Primary Endpoints	Proportion of patients with symptomatic intracranial haemorrhage (SICH) within 48 hours after EVT		
Secondary Endpoints	Proportion of patients with asymptomatic intracranial haemorrhage (aSICH) within 48 hours after EVT;		
	 Incidence of any complications (including non-hemorrhagic serious adverse events such as gastrointestinal bleeding, urethral bleeding, oral or nasal mucosal bleeding, and subcutaneous hematoma, etc; or complications related to procedures and devices such as arterial rupture, arterial dissection, implantation failure, stent fracture, vascular puncture site complications, vasospasm, and device malposition, etc); Incidence of any adverse events (including cerebral hernia, pneumonia, 		
	respiratory failure, circulatory failure, stress ulcer, secondary epilepsy, urinary tract infection, sepsis, renal failure, acute coronary syndrome, venous thrombosis, and psychiatric symptoms, etc);		
	4) Proportion of patients with gastrointestinal haemorrhage within 7 days after EVT;		

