Proportion of patients with pneumonia. 1) Inclusion Criteria Age 18 years; 2) The time from onset to randomization was within 12 hours; 3) Anterior circulation ischemic stroke was preliminarily determined according to clinical symptoms or imaging examination: 4) Occlusion of the intracranial internal carotid artery, the M1- or M2-segment of the middle cerebral artery confirmed by CT angiography (CTA), MR angiography (MRA), or digital subtraction angiography (DSA); Baseline National Institutes of Health Stroke Scale (NIHSS)>6; 5) 6) Baseline Alberta Stroke Program Early CT Score (ASPECTS)<6: Planned treatment with endovascular therapy (EVT); Informed consent obtained from patients or their legal representatives. Intracranial hemorrhage confirmed by cranial computed tomography (CT) or **Exclusion Criteria** magnetic resonance imaging (MRI). 2) mRS score ≥ 2 before onset. 3) Pregnant or lactating women. 4) Allergic to contrast agents or glucocorticoids. 5) Participating in other clinical trials. Systolic blood pressure >185 mmHg or diastolic pressure >110 mmHg, and oral antihypertensive drugs cannot control. Genetic or acquired bleeding constitution, lack of anticoagulant factors, or oral anticoagulants and INR > 1.7. 8) Blood sugar < 2.8 mmol/L (50 mg/dl) or > 22.2 mmol/L (400 mg/dl), platelet $< 90 \times 10^{9}/L$. The artery is tortuous so that the thrombectomy device cannot reach the target vessel. 10) Bleeding history (gastrointestinal and urinary tract bleeding) in recent 1 month 11) Chronic hemodialysis and severe renal insufficiency (glomerular filtration rate < 30 ml/min or serum creatinine > 220 umol/L [2.5 mg/ dL]). 12) Life expectancy due to any advanced disease < 6 months. Follow-up is not expected to be completed. 13) Intracranial aneurysm and arteriovenous malformation. 14) Brain tumors with imaging mass effect. 15) Systemic infectious disease. **Treatments** The emergency interventional team is on call 24 hours a day, 7 days a week. Each sub-center selects patients based on the above inclusion and exclusion criteria, and assigns them to either the intravenous methylprednisolone sodium succinate + endovascular treatment group (experimental group) or the placebo (i.e., intravenous methylprednisolone sodium succinate simulator) + endovascular treatment group (control group) in a 1:1 ratio by a web-based APP on mobile phone or computer. Randomization will be stratified by participating centres permutation block size of 8. After patients agree to participate and obtain a random number, they will receive intravenous methylprednisolone sodium succinate or placebo treatment as soon as possible, preferably before the establishment of arterial access and no later than 2 hours after the completion of endovascular treatment. Relevant time points (accurate to the minute) will be recorded truthfully and accurately. The effectiveness and safety of the two treatment regimens will be observed and evaluated.

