Intravascular therapy helps improve the prognosis of patients with acute ischemic stroke, but postoperative complications such as hemorrhagic transformation and malignant brain edema are important causes of death. Hemorrhagic transformation refers to the hemorrhage in the ischemic lesion caused by a variety of underlying mechanisms during ischemic stroke, among which the incidence of hemorrhagic transformation after intravascular treatment is about 46%-49.5%, and the incidence of symptomatic hemorrhagic transformation is 2%-16%. He is currently believed that oxidative stress, inflammatory response, and blood-brain barrier damage may be the underlying mechanisms of hemorrhagic transformation after intravascular treatment of acute ischemic stroke. Malignant cerebral edema is the main cause of early death and disability after ischemic stroke, with an incidence of 10%-78% in patients with ischemic stroke. It is characterized by a malignant course accompanied by severe cerebral edema, leading to cerebral hemia, death, or severe neurological dysfunction. The main mechanisms of cerebral edema after ischemic stroke include early cytotoxic edema and late vasogenic edema. Early cytotoxic edema is due to increased permeability of brain tissue and failure of Na+/K+ pump caused by ischemia and hypoxia, resulting in cell swelling, narrowing of extracellular space, and increased brain volume. Tissue necrosis and basement membrane degeneration cause damage to the blood-brain barrier, and 4-6 hours later, serum proteins begin to enter the brain from the blood,

inducing vasogenic edema and further increasing brain water content. In addition, reperfusion of the blood supply artery in the infarct area leads to more water passing through the damaged blood-brain barrier, combined with ischemia-reperfusion and hyperperfusion injury after mechanical thrombectomy, further exacerbating vasogenic edema, which peaks 1 to several days after ischemia and leads to malignant cerebral edema. Therefore, reducing complications such as hemorrhagic transformation and malignant cerebral edema after intravascular therapy is the key to ultimately reducing the mortality rate of patients with acute ischemic stroke.

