Glucocorticoids are the most widely used and effective anti-inflammatory and immunosuppressive agents in clinical practice. They have the functions of stabilizing cell membranes, regulating the balance of water and electrolytes inside and outside cells, reducing the production of cerebrospinal fluid, and exerting non-specific antioxidant effects. They can also prevent cell membrane phospholipids from being damaged by free radicals, actively regulate and restore blood circulation in damaged brain tissue, and reduce cerebral edema.²¹ Methylprednisolone sodium succinate for injection is a medium-acting glucocorticoid that is widely used in clinical practice due to its small side effects and strong ability to penetrate the blood-brain barrier. Early basic research found that early combination therapy with methylprednisolone sodium succinate for injection can significantly increase cerebral blood flow reperfusion and reduce brain damage in a cat ischemia-reperfusion model.²² Recent studies have also shown that early combination therapy with methylprednisolone sodium succinate for injection can improve neurological deficits and increase the survival rate of newborn neurons by inhibiting neuronal apoptosis and down-regulating inflammatory responses in a rat ischemia-reperfusion model.^{23,24} A recent randomized controlled clinical trial (MARVEL) published in JAMA suggests that early combination therapy with methylprednisolone sodium succinate can reduce mortality and the incidence of symptomatic intracranial hemorrhage after intravascular therapy for patients with acute ischemic stroke. However, this study excluded patients with large infarct core strokes (ASPECTS score <6) who have more severe clinical symptoms and higher mortality and disability rates. 25 Currently, there is not enough evidence to support the safety and efficacy of early combination therapy with methylprednisolone sodium succinate for acute large core infarct reperfusion. To address this dilemma, there is an urgent need to conduct research specifically on this subset of patients.

Therefore, we intend to adopt a multi-center, prospective, randomized, double-blind controlled trial design to explore whether early combination therapy with methylprednisolone sodium succinate can improve the clinical prognosis of patients with acute large core infarcts based on revascularization.

2. Study Objectives

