10.2.2. Secondary Safety Endpoints

- Proportion of patients with asymptomatic intracranial haemorrhage (aSICH) within 48 hours after EVT; 1)
- 2) The incidence of non-intracranial hemorrhage complications (including gastrointestinal bleeding, urethral bleeding, oral or nasal mucosal bleeding, and subcutaneous hematoma, etc.);
- The incidence of non-hemorrhagic serious adverse events (including cerebral hernia, pneumonia, respiratory failure, circulatory failure, stress ulcer, secondary epilepsy, urinary tract infection, sepsis, renal failure, acute coronary syndrome, venous thrombosis, and psychiatric symptoms, etc.);
- 4) Operation and device-related complications (including artery rupture, artery dissection, implant failure, stent

Release date: July 23, 2024

fracture, vascular puncture site complications, vasospasm, and device not in place, etc.);

5) Glucocorticoid-related adverse events (including insulin use in hospital, new-onset diabetes, lung infection during hospitalization, gastrointestinal bleeding within 7 days after surgery, etc.).

11. Adverse Events

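### Section 10.2.2 item 3 pools cerebral hernia, which the drug is meant to reduce, with infections it may increase; sepsis, urinary tract infection and total infection get no separate comparison

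*Combined protocol and SAP*

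**What the plan says.** Section 10.2.2 item 3 defines one secondary safety endpoint: "The incidence of non-hemorrhagic serious adverse events (including cerebral hernia, pneumonia, respiratory failure, circulatory failure, stress ulcer, secondary epilepsy, urinary tract infection, sepsis", followed by renal, coronary, thrombotic and psychiatric events. The synopsis has the same list under a wider label: "Incidence of any adverse events (including cerebral hernia, pneumonia", and so on.

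Section 1 (Study Background) sets out the expected effects:

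- Malignant edema involves "severe cerebral edema, leading to cerebral hemia, death, or severe neurological dysfunction" (the misspelt word is evidently hernia).
- The Background adds that "reducing complications such as hemorrhagic transformation and malignant cerebral edema after intravascular therapy is the key to ultimately reducing the mortality rate".
- Glucocorticoids are said to "actively regulate and restore blood circulation in damaged brain tissue, and reduce cerebral edema".
- The same paragraph opens: "Glucocorticoids are the most widely used and effective anti-inflammatory and immunosuppressive agents in clinical practice".

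Two other places bear on infection. Section 10.2.2 item 5 is a separate steroid endpoint: "Glucocorticoid-related adverse events (including insulin use in hospital, new-onset diabetes, lung infection during hospitalization, gastrointestinal bleeding within 7 days after surgery, etc". The synopsis list of secondary safety endpoints ends with a stand-alone item, "Proportion of patients with pneumonia", which Section 10.2.2 does not carry.

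Section 12.3 gives a chi-square or Fisher's exact test for categorical data. Neither Section 10.2.2 nor Section 12 says that the components of item 3 will be compared or tabulated separately.

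**The concern.** Item 3 counts in one direction events that the protocol's own rationale expects to move in two. Hernia is a downstream result of the edema the drug is given to reduce; malignant edema is itself secondary efficacy endpoint 14. Pneumonia, urinary tract infection and sepsis are plausible harms of an immunosuppressive drug, and item 5 itself classes lung infection as glucocorticoid-related. If a patient counts once for any listed event, a benefit on hernia offsets a harm on infection, and a near-null result cannot be told apart from no effect on either.

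Safety is one of the two stated objectives (Section 2), and the Background says evidence in large-core patients is insufficient. The infection profile is therefore a result that readers will look for.

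**Working it through.** **1. Number per arm.** From Section 5: mortality 38% v 29%, two-sided alpha 0.05, power 80%. With unpooled variance, n = (1.960 + 0.842)² × (0.38×0.62 + 0.29×0.71) / 0.09² = 427.8, so 428 per arm and 856 in total. Then 428/0.95 = 450.5, so 451 per arm and 902 in total. Both stated figures reproduce. I use 428 per arm below.

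**2. Where each infection can be seen.**

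| Event | 10.2.2 item 3 (with hernia) | 10.2.2 item 5 (without hernia) | Own endpoint |
|---|---|---|---|
| Pneumonia / lung infection | yes | yes, pooled with insulin use, new diabetes and gastrointestinal bleeding | synopsis only |
| Urinary tract infection | yes | not named | none |
| Sepsis | yes | not named | none |
| Any infection | no | no | none |

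Item 5 ends in an open-ended etc., so whether it takes in the other infections is undefined.

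**3. Size of the masking (illustration).** The documents give no rates for hernia, infection or the other events; every rate here is an assumption. I read incidence as the proportion of patients with at least one listed event. With independent components:

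pooled rate = 1 − (1 − hernia)(1 − infection)(1 − other)

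power = Φ[(d − 1.96·SE₀)/SE₁], with d the absolute difference, SE₀ from the average rate and SE₁ from the two rates.

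- Infection alone, 35% v 43%: d = 0.080, SE₀ = 0.0333, SE₁ = 0.0332, power = Φ(0.44) = 67%.
- Pooled with hernia 20% v 14%: control 1 − 0.80×0.65 = 0.480; active 1 − 0.86×0.57 = 0.510. d = 0.030, SE₀ and SE₁ both 0.0342, power = Φ(−1.09) = 14%.

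With infection fixed at 35% v 43%:

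| Hernia, control to active | Other events (both arms) | Pooled rates | Power |
|---|---|---|---|
| 20% to 14% | 0% | 48.0% v 51.0% | 14% |
| 20% to 14% | 30% | 63.6% v 65.7% | 9% |
| 15% to 10% | 0% | 44.8% v 48.7% | 21% |
| 15% to 10% | 30% | 61.3% v 64.1% | 13% |
| 25% to 18% | 0% | 51.2% v 53.3% | 9% |
| 25% to 18% | 30% | 65.9% v 67.3% | 6% |
| 20%, unchanged | 0% | 48.0% v 54.4% | 47% |
| 20%, unchanged | 30% | 63.6% v 68.1% | 28% |

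**4. Sensitivity to independence.** For hernia 20% to 14% with no other events, a latent (bivariate normal) correlation between hernia and infection gives pooled power of 14% at 0, 23% at 0.5, 32% at 0.7 and 54% at 0.9. If every hernia patient also has an infection, the pooled rate equals the infection rate and nothing is lost. Negative correlation would act the other way.

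**5. Item 5.** Lung infection at 35% v 43%, pooled with unrelated item 5 events at 20% or 40% in both arms, gives 48.0% v 54.4% (power 47%) or 61.0% v 65.8% (power 31%). Item 5 has no opposing component, but it still dilutes.

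**The case against.** The strongest reply is that the plan already separates steroid harm from intended benefit. Item 5 is a glucocorticoid endpoint that names lung infection and leaves hernia out; the synopsis gives pneumonia its own line; edema and craniectomy are efficacy items 14 and 15. The primary safety endpoint is symptomatic intracranial haemorrhage, and no section rests the steroid safety conclusion on item 3. All adverse events are recorded (Section 11.3), the DSMB reviews all clinical and safety endpoint events (Section 13.2), and Section 12.1.1 leaves the detailed methods to an analysis plan finalised before database lock. Component rows are unstated, not excluded.

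Most of this stands. A reader might infer from item 3 that the trial will report the steroid's infection risk as null. The documents do not support that: item 5 and the synopsis pneumonia endpoint both give a view of lung infection that hernia cannot offset.

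The power figures are also fair to challenge. The listed events probably cluster in the sickest patients, which weakens the masking (step 4), and nothing in the documents supports rates of 35% to 43% under a label restricted to serious events. Without an edema benefit, the loss is the ordinary dilution of any overall event rate.

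The reply does not cover sepsis, urinary tract infection or total infection. It also relies in part on a synopsis endpoint that the endpoint section omits.

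**Conclusion.** The point holds as a limited one about a secondary safety endpoint. Item 3 mixes an event the drug is intended to reduce with events it may increase, so it can read near null under real opposing effects and it dilutes an infection signal even without them. Sepsis and urinary tract infection are named nowhere else, and there is no all-infection comparison. Lung infection is partly covered, by a mixed item 5 and by a pneumonia endpoint present only in the synopsis.

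Under the assumed rates and independence, power for an 8-point rise in infection drops from 67% to between 6% and 21% with an opposing hernia effect, and to between 28% and 47% without one. These figures show what is possible and do not forecast this trial; positive correlation between hernia and infection would shrink the loss. The primary analysis and sample size are not touched. The point concerns endpoint definition and reporting, not patient management.

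**What to change.** 1. Prespecify an any-infection safety endpoint (pneumonia, urinary tract infection or sepsis), with a risk difference and confidence interval.
2. Report every component of items 3 and 5 by arm, with cerebral hernia on its own row. Plain rows are safer than a disease-course subgroup: respiratory or circulatory failure can follow an infection, and stress ulcer and psychiatric symptoms should stay visible in the steroid safety review.
3. Keep pooled item 3 as a descriptive line, and state that it will not be used alone to conclude that the steroid is safe.
4. Carry the synopsis pneumonia endpoint into Section 10.2.2, and settle whether the hernia and pneumonia list covers any adverse events or only non-hemorrhagic serious ones.

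The cost is protocol and analysis-plan wording, a few table rows and a few more safety comparisons. All the events are already to be recorded, so no new data are needed. Fixing the definitions before unblinding also avoids choosing components after the results are seen.

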4.2. Exclusion Criteria

- 1) Intracranial hemorrhage confirmed by cranial computed tomography (CT) or magnetic resonance imaging (MRI).
- 2) mRS score \geq 2 before onset.
- 3) Pregnant or lactating women.
- 4) Allergic to contrast agents or glucocorticoids.
- 5) Participating in other clinical trials.
- 6) Systolic blood pressure >185 mmHg or diastolic pressure >110 mmHg, and oral antihypertensive drugs cannot control.
- Genetic or acquired bleeding constitution, lack of anticoagulant factors, or oral anticoagulants and INR > 1.7.
- 8) Blood sugar < 2.8 mmol/L (50 mg/dl) or > 22.2 mmol/L (400 mg/dl), platelet $< 90 \times 10^{9} \text{/L}$.
- 9) The artery is tortuous so that the thrombectomy device cannot reach the target vessel.
- 10) Bleeding history (gastrointestinal and urinary tract bleeding) in recent 1 month.
- 11) Chronic hemodialysis and severe renal insufficiency (glomerular filtration rate < 30 ml/min or serum creatinine > 220 umol/L [2.5 mg/ dL]).
- 12) Life expectancy due to any advanced disease < 6 months.
- 13) Follow-up is not expected to be completed.
- 14) Intracranial aneurysm and arteriovenous malformation.
- 15) Brain tumors with imaging mass effect.
- 16) Systemic infectious disease.

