4.4. Privacy Protection

completely stored in the hospital where they receive treatment, and laboratory test reports and other examination results will be recorded in the patients' medical records. Only the investigators, ethics committees, and food and drug administration departments of this study will be allowed to access patients' medical records. Any public reports on the results of this study will not disclose the personal identities of patients. We will make every effort to protect the privacy of patients' personal medical information within the limits allowed by law.

According to medical research ethics, apart from personal privacy information, trial data will be available for public inquiry and sharing. Inquiry and sharing will be limited to web-based electronic databases to ensure that no personal privacy information is leaked.

5. Sample Size Calculation

Based on the research results from published literature and combined with clinicians' experience, the 90-day mortality rates for the intravenous methylprednisolone sodium succinate + endovascular treatment group (experimental group) and the placebo + endovascular treatment group (control group) are estimated to be 29% and 38%, respectively. Assuming a 1:1 ratio for the sample sizes of the two groups, a two-sided α of 0.05, and a power of 80%, the estimated sample size is 856 patients. Considering an expected dropout rate of 5%, the maximum estimated sample size, calculated using PASS 15.0, is 902 patients, with 451 patients in each of the intravenous methylprednisolone sodium succinate + endovascular treatment group (experimental group) and the placebo + endovascular treatment group (control group).

6. Randomization

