9.1. Collection of Baseline Data

Written informed consent must be obtained from the patient or their family members before implementing the research steps required by the protocol. The patient should be given a copy of the signed informed consent form to keep.

During the screening period, the following data should be evaluated and recorded in the original medical records and the single-disease database (intended to use the Yidu Cloud Scientific Research Collaboration Platform):

- 1) Patient information and informed consent form;
- 2) Evaluation of inclusion and exclusion criteria;
- 3) Demographic characteristics;
- 4) Past medical history and related treatment history;
- 5) For women of childbearing age: urine pregnancy test.

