11.1. Definition

11.1.1. Definition of Adverse Events (AE)

AE refers to an adverse medical event that occurs after a patient or clinical trial participant receives a drug or device, but it does not necessarily have a causal relationship with the treatment.

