12.2.4. Missing Data

12.3. Statistical Analysis Methods

Statistical tests will be performed using a two-sided significance level of 0.05 for indicators evaluated with superiority. Differences with a P-value ≤ 0.05 will be considered statistically significant.

Statistical analysis will be conducted on baseline indicators (such as medical history) and demographic characteristics. Intent-to-treat analysis will be used for statistical analysis of trial efficacy, with the per-protocol dataset (i.e., data from patients who meet all trial protocol criteria) as a reference.

Quantitative data will be described using means, medians, standard deviations, maximum and minimum values, and 25th and 75th percentiles. Comparisons between two groups will be made using the independent t-test or Mann-Whitney U test. Categorical or ordinal data will be described using frequencies and proportions. Comparisons between two groups for categorical data will be made using the chi-square test or Fisher's exact test, and for ordinal data, the Mann-Whitney *U* test will be used.

Previous studies have suggested that the following factors may affect the 90-day mRS score, and this study plans to conduct subgroup analysis based on these variables.

- 1) Age;
- 2) Gender:
- 3) Time of onset;
- 4) NIHSS score:
- 5) ASPECTS score;
- 6) TOAST classification [22];
- 7) Vascular occlusion site;
- 8) Collateral circulation score:
- 9) Anesthesia method:
- 10) Intravenous thrombolysis.

13. Quality Control and Assurance

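### Section 10.2.2 item 5 counts any in-hospital insulin as a steroid-related event, so patients who were already on insulin at entry dilute the comparison for that component

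*Combined protocol and SAP*

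**What the plan says.** Item 5 of the secondary safety endpoints (section 10.2.2) begins "Glucocorticoid-related adverse events (including insulin use in hospital, new-onset diabetes" and goes on to lung infection in hospital, early gastrointestinal bleeding and an open-ended remainder. The diabetes component is limited to new onset. The insulin component beside it has no such limit.

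On glucose, section 4.2 excludes only "Blood sugar < 2.8 mmol/L (50 mg/dl) or > 22.2 mmol/L (400 mg/dl". No criterion in sections 4.1 or 4.2 bars known diabetes or current insulin treatment.

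The general definition in section 11.1.1 says "AE refers to an adverse medical event that occurs after a patient or clinical trial participant receives a drug or device", with no rule for a treatment already in use at entry. Section 9.1 has sites record "Past medical history and related treatment history" at screening, but no endpoint refers back to it. Section 12.3 states "Comparisons between two groups for categorical data will be made using the chi-square test or Fisher's exact test", without adjustment, and neither diabetes nor insulin is among its subgroup variables.

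**The concern.** Insulin use stands in this endpoint as a marker of steroid-induced hyperglycaemia. It can do that only in patients who were not on insulin beforehand. A long-term user who carries on with insulin in hospital is recorded as an event whichever treatment was given, and says nothing about the drug.

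Randomisation spreads such patients evenly on average, so they do not bias the test under the null hypothesis. They add the same number of uninformative events to both arms, which reduces the contrast. For an efficacy endpoint that would be conservative. For a harm endpoint it favours a report of no excess harm. Item 5 is the only listed endpoint with metabolic components, so no other endpoint would make up for a weak reading here.

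**Working it through.** **The plan's own figure.** Section 5 assumes 90-day mortality rates that "are estimated to be 29% and 38%, respectively" and says that with "a two-sided α of 0.05, and a power of 80%, the estimated sample size is 856 patients". With unpooled variance, n per arm = (1.960 + 0.842)² × (0.38 × 0.62 + 0.29 × 0.71) / 0.09² = 7.849 × 0.4415 / 0.0081 = 427.8, so 428 per arm and 856 in all. Then 856 / 0.95 = 901.05, rounded up to 902, or 451 per arm. The figure reproduces. It concerns mortality only, and is used here just for the arm size of 451.

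**Inputs for the insulin component.**
- 451 patients per arm (section 5).
- Two-sided 5% test of two proportions (section 12.3).
- Share q on insulin at entry, equal in both arms: not in the documents, assumed 2% to 20%.
- New insulin use among patients not on it at entry: not in the documents, assumed 10% on placebo and 18% on methylprednisolone (risk ratio 1.80).
- All patients on insulin at entry continue it in hospital and are counted.

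**Dilution.** The recorded rate in an arm with new-use rate p is q + (1 − q)p. The recorded risk difference is therefore (1 − q)(p_active − p_placebo), and the recorded risk ratio is [q + (1 − q)p_active] / [q + (1 − q)p_placebo]. For any q above zero and p_active above p_placebo, this ratio lies closer to 1 than p_active / p_placebo.

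**Power.** Power = Φ[(d − 1.96 × se0) / se1], where d is the risk difference, se0 the pooled and se1 the unpooled standard error.

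Worked case, q = 10%:
- Any use: placebo 0.10 + 0.90 × 0.10 = 0.190; active 0.10 + 0.90 × 0.18 = 0.262; d = 0.072. With 451 per arm, se0 = 0.02785 and se1 = 0.02775. Power = Φ[(0.072 − 0.0546) / 0.02775] = Φ(0.63) = 73%.
- New use among non-users: 0.10 versus 0.18, d = 0.080. With 451 × 0.90 = 406 per arm, se0 = 0.02436 and se1 = 0.02419. Power = Φ[(0.080 − 0.0477) / 0.02419] = Φ(1.33) = 91%.

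| q | Any use, placebo vs active | Risk difference | Risk ratio | Power, any use | Non-users per arm | Power, new use (RR 1.80) |
|---|---|---|---|---|---|---|
| 2% | 11.8% vs 19.6% | 7.8 points | 1.66 | 90% | 442 | 93% |
| 5% | 14.5% vs 22.1% | 7.6 points | 1.52 | 84% | 428 | 92% |
| 10% | 19.0% vs 26.2% | 7.2 points | 1.38 | 73% | 406 | 91% |
| 20% | 28.0% vs 34.4% | 6.4 points | 1.23 | 55% | 361 | 87% |

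With q = 0 both versions have 93% power.

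**Sensitivity to the assumed rates, at q = 10%.** New use of 10% versus 17% gives 63% for any use and 83% for new use. For 15% versus 23% the figures are 68% and 83%. For 20% versus 30% they are 82% and 91%. In every case run, the restricted version has more power despite fewer patients.

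**The case against.** **Reading of the definition.** Item 5 concerns adverse events, and section 11.1.1 requires an adverse medical event after the drug or device is received, so unchanged long-term insulin need not qualify. Section 12.1.1 also leaves derivation rules to an analysis plan finalised before database lock. This stands in part: the gap is an unstated derivation that can still be closed. It does not repair the text, because item 5 names insulin use itself as the event, and sites could code it differently.

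**Size.** Every insulin rate is assumed. With few prior users the loss is slight: 90% against 93% at 2%. This stands.

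**Stakes.** Any use is still a valid randomised comparison of insulin need, with no inflation of type I error. It is one component of a secondary safety endpoint with no stated power. Pneumonia and gastrointestinal bleeding are also covered elsewhere in section 10.2.2 and in the synopsis. This stands, and limits the point to the metabolic signal.

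**Stronger readings that a reader might infer.**
- That baseline insulin use dominates a steroid-harm composite. The documents do not say that item 5 is pooled into one incidence; it only lists event types. The figures above are for the insulin component alone.
- That new-onset diabetes cannot be established with the planned data. Table 1 has medical history at screening, and adverse events and treatment medication at day 90, so a diagnosis or a new antidiabetic drug could be recorded there.
- That a patient admitted with high glucose is automatically an event. Such a patient counts only if insulin is given, and no section says that it will be.

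**Conclusion.** The concern holds for the insulin component of item 5. As written, it counts patients who continue insulin in both arms, multiplies the risk difference by (1 − q), and moves the risk ratio toward no harm. The direction follows from the text and arithmetic, provided that patients on insulin at entry continue it in hospital and are counted.

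The size depends on assumptions that the documents cannot settle. With new use of 10% versus 18%, the loss of power against the restricted definition is about 3 points at 2% prior use, 8 at 5%, 17 at 10% and 33 at 20% (from unrounded powers). It is worth correcting because the change is cheap and the error runs in the unsafe direction. The point does not reach the primary endpoint, the sample size, or the other components of item 5.

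**What to change.** In section 10.2.2 item 5 and in the analysis plan, before database lock:
1. Define the component as insulin newly started after the first study dose, in patients not using insulin at randomisation. The denominator is all such patients in each arm. It is fixed at randomisation, so the comparison remains a randomised one.
2. Keep any in-hospital insulin use, in all patients, as a supportive analysis.
3. Report each component of item 5 separately by arm.
4. Confirm that the case report form captures insulin use at entry explicitly within the treatment history, and the start time of any new insulin. Insulin begun between randomisation and the first dose is not an event under this wording, and the plan should say so.

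The cost is wording plus one derived baseline variable, with no new test or visit and no change to patient management. There are two downsides. The denominator shrinks to 451 × (1 − q) per arm, for example 361 at 20% prior use. And insulin escalation in existing users is not counted in the main version of the component; nor does the supportive any-use analysis show it, since those patients count there whatever their dose.
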